9.2 Treatment Phase

A total of three weeks of therapy will be planned. Serial liver biopsies will be obtained, with the first performed prior to initiating therapy and the second performed on Day 20 (\pm 2 days). Following completion of the 3 consecutive weeks of treatment, the study treatment period will conclude. In order to secondarily assess clinical benefit, repeat CT imaging will be assessed at day 46 (\pm 3 days). If a patient completes therapy and a decision is made to pursue a further alternate treatment, the subject will come off study; however, in this circumstance, assessment of the next clinical staging study will be requested for determination of RECIST parameters.

Schema

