10.3 General Concomitant Medication and Supportive Care

Additional chemo-, immune-, and radiotherapies are not permitted during the active treatment period of this trial. Palliative radiotherapy may be permitted for symptomatic control of pain from bone metastases following discussion with the Principal Investigator, provided that the radiotherapy does not affect target lesions.

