10.4 Duration of study treatment

A total of 3 weeks of treatment is planned. A repeat liver biopsy will be performed at Day 24 (\pm 4 days) after completion of protocol therapy and the study biopsy; the patient will then proceed onto the follow-up period.

The participant may stop treatment earlier than planned in the event that the following occurs:

- Disease progression
- Unacceptable toxicity
- Withdrawal from study
- Intercurrent illness that prevents further administration of treatment
- Participant non-compliance with study requirements

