11.3 Pathology

Fresh Biopsy Samples

At each liver biopsy collection time point, 6 total cores will be obtained, including at least 5 tumor cores and 1 additional core of surrounding liver tissue (to enhance the stringency of our assays). 4 cores of tumor and 1 core of surrounding liver tissue will be placed in Dulbecco's Phosphate-Buffered saline, and 1 core of tumor will be placed in formalin, and processed to FFPE block per institute standard.

Pre- and post-treatment cores should be obtained from the same lesion. If non-necrotic lesions are present at baseline, they should be prioritized for biopsy, with the necrotic lesions being

PROTOCOL TITLE: Phase 2A Study Evaluating a Chemokine-Modulatory Regimen in Patients with Colorectal Cancer Metastatic to the Liver

avoided per the interventional radiologists' discretion. Any biopsy core which appears as necrotic should be discarded.

Label the samples with study-specific subject ID number, clinical study number, protocol time point and, protocol day. Phosphate-Buffered saline, will be supplied by [name] lab and sample will be kept at ambient temperature. Samples in Dulbecco's Phosphate-Buffered Saline will be sent to [name] lab upon completion of processing (preferably ASAP within 2 hours of collection, but within 4 hours of collection is allowed). Once the remaining core has been processed to FFPE block, it will be delivered to OmniSeq

- The changes in the ratio between CTL marker (CD8a gene expression) to Treg markers (FoxP3 gene expression), using RT-PCT will be considered as a primary endpoint of efficacy.

Additional correlative studies may be performed on the same material:

- Comparison (using RT-PCR, Immunofluorescence [IF] and immunohistochemistry [IHC] on serial sections) of the metastatic tissue specimen with regard to total numbers of infiltrating T cells, their CD4/CD8 ratios, frequencies of FoxP3 cells, and the expression of chemokine receptors on CD4⁺ and CD8⁺ T cells (CXCR3, CCR5, CCR4, CCR6, and CXCR4).
- Evaluate the local expression of T_{eff}-attracting chemokines (CCR5, CXCL9, CXCL10 and CXCL11) and T_{reg}-favoring chemokines (CCL22 and CXCL12) using IF and RT-PCR.
- Additional tissue evaluations, including OmniSeq Immune Report card, NanoString or similar, may be performed, depending on the availability of funding.

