2. At each time point, Physical exam to include assessment of Head/Ears/Eyes/Nose/Throat (HEENT), Skin, Chest/Lungs, Heart, Neck/lymph nodes, Abdomen including liver/spleen, Extremities and weight. Height to be collected at screening only. Physical exam does not need to be repeated on Day 1 if performed within 3 days prior to Day 1.

3. CBC with auto differential.

4. Glucose, BUN, creatinine, sodium, potassium, chloride, CO₂, calcium, total protein, albumin, alkaline phosphatase, AST, ALT, total bilirubin, amylase, lipase.

5. Within 7 days of Day 1 and as clinically indicated once on treatment in women of child-bearing potential only.

6. Blood (60cc) for in vitro assays will be drawn as outlined in section 11.2.

6^a. Day 3 only within 1 hour after end of infusion

7. Within 28 days prior to Day 1.

8. Vital Signs (blood pressure, pulse, respiratory rate and temperature) will be obtained at screening and end of treatment visits. On dosing days, vital signs will be obtained pre-treatment, 30 and 60 minutes post Rintatolimod (± 5 minutes).

9. Patients will be followed for survival status for 12 months after end of treatment visit. Phone contact/chart review is acceptable.

10. Restaging imaging CT/MRI to be performed on day 46 ± 3 days. If this scan demonstrates stable disease/response, patients will continue in follow-up with CT imaging every 8 weeks until progression, clinical deterioration or withdrawal from study. If in the clinical judgement of the treating team, it is in the best interest of the patient to pursue another therapeutic option, the patient will come off study and CT imaging will be obtained only as SOC/protocol.

11. Once every 3 months for up to 12 months after EOT visit to ascertain survival – both chart review and/or phone contact are acceptable

PROTOCOL TITLE: Phase 2A Study Evaluating a Chemokine-Modulatory Regimen in Patients with Colorectal Cancer Metastatic to the Liver

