Appendix G

RECIST 1.1 Criteria

Objective Tumor Response

All protocol-defined imaging studies must be performed at the investigative site or sponsor-approved facility using protocol-defined parameters. The same method of assessment and the same technique should be used to characterize each identified and reported lesion at baseline and during follow-up. RECIST 1.1 will be used to assess objective tumor response.

Target Lesions

All measurable lesions up to a maximum of 2 lesions per organ and 5 lesions in total, representative of all involved organs, will be identified as target lesions and recorded and measured at baseline. Target lesions will be selected on the basis of their size. Lesions with the longest diameter (short axis for lymph nodes) and are ≥ 10 mm (CT and MRI), ≥ 15 mm lymph nodes, > 20 mm CXR and are for accurate repetitive measurements (either by imaging techniques or clinically) will be chosen. A sum of the longest diameter (short axis for lymph nodes) of all target lesions will be calculated and reported as the baseline sum diameters. This will be used as reference to further characterize the objective tumor response of the measurable dimension of the disease.

- **Complete Response (CR):** Disappearance of all target lesions. Any lymph nodes must have a reduction in short axis to < 10 mm. Changes in tumor measurements must be confirmed by repeat studies performed no less than 6 weeks after the criteria for response are first met.
- **Partial Response (PR):** At least a 30% decrease in the sum of diameters of target lesions, taking as reference the baseline sum diameters. Changes in tumor measurements must be confirmed by repeat studies performed no less than 6 weeks after the criteria for response are first met.
- **Progressive Disease (PD):** At least a 20% increase in the sum of diameters of target lesions, taking as references the smallest sum on study (this includes the baseline sum if that is the smallest on study). In addition to the relative increase of 20%, the sum must also demonstrate an absolute increase of at least 5 mm. The appearance of one or more new lesions is also considered progression.
- **Stable Disease (SD):** Neither a sufficient shrinkage to qualify for PR nor sufficient increase to qualify for PD, taking as reference the smallest sum diameter while on study. Participants having a documented response with no confirmation of the response will be listed with stable disease.

Non-Target Lesions

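### A lesion cored twice for research can be, and with only one or two measurable liver lesions must be, a RECIST target, so a procedural size change could cause a false progression in exploratory PFS

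*Combined protocol and SAP*

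**What the plan says.** Section 11.3 (Pathology) sets the sampling. At each biopsy, "6 total cores will be obtained, including at least 5 tumor cores and 1 additional core of surrounding liver tissue". It adds that "Pre- and post-treatment cores should be obtained from the same lesion". The lesion is chosen for tissue quality: "If non-necrotic lesions are present at baseline, they should be prioritized for biopsy". Whether it is also a RECIST target is not mentioned.

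Section 9.2 gives the timing of the two biopsies: "the first performed prior to initiating therapy and the second performed on Day 20", with a window of 2 days either side. Section 10.4 differs: "A repeat liver biopsy will be performed at Day 24", with a window of 4 days either side.

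Appendix G takes all measurable lesions as targets, up to two per organ and five in total, and states that "Target lesions will be selected on the basis of their size". It neither excludes nor flags a lesion that is sampled for research. The inclusion criteria in Section 3.1 ask for measurable disease and for a liver metastasis that can be biopsied, but not for a measurable lesion other than the biopsied one.

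Section 10.3 permits palliative radiotherapy "provided that the radiotherapy does not affect target lesions". No similar sentence covers biopsy.

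The study calendar in Appendix F allows the baseline scan "Within 28 days prior to Day 1" and places the first biopsy between Day -14 and Day -1. It sets no order between them. The first response scan is on Day 46, within 3 days either side.

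**The concern.** RECIST reads a change in the target sum as tumour growth or shrinkage. Bleeding, swelling or scarring after repeated coring could also change the diameter of a target lesion, and Appendix G gives the radiologist no rule for telling the two apart.

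A procedural enlargement is the more exposed direction. Appendix G asks for a repeat study before a complete or partial response counts, but has no such requirement for progression in target lesions. Under Sections 9.3 and 11.1.6, protocol imaging continues after Day 46 only for stable disease or response, and Appendix G counts best response only up to progression. A false progression at Day 46 would therefore fix the PFS event, end the protocol scans and shut out any later response.

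**Working it through.** **The plan's own figure.** The plan gives no figure on this point. Its one power statement (Section 19.2: n = 12, 0.77 SD, one-sided level 0.1, 90% power) is reproduced by the noncentral t distribution (df = 11, noncentrality 0.77 × √12), which gives 0.900. That statement concerns the CD8 endpoint, and nothing below changes it.

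**Step 1: number of cores (Section 11.3).** 2 biopsies × at least 5 tumour cores = at least 10 tumour cores from one lesion, if both biopsies are done.

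**Step 2: when overlap is forced.** Appendix G takes every measurable lesion up to two per organ. With one or two measurable liver lesions, a measurable biopsied lesion is a target unless the cap of five in total intervenes. With three or more, overlap depends on whether the lesion chosen for biopsy is also among those chosen by size.

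**Step 3: timing against the scans.** From the second biopsy to the Day 46 scan:
- Section 9.2 (Day 20 ± 2): 46 − 20 = 26 days; range 43 − 22 = 21 to 49 − 18 = 31.
- Section 10.4 (Day 24 ± 4): 46 − 24 = 22 days; range 43 − 28 = 15 to 49 − 20 = 29.

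The second biopsy therefore falls 15 to 31 days before the scan on either reading. The first also falls between the baseline and Day 46 scans if the baseline scan was done before it, which the calendar allows.

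**Step 4: change needed to alter the call.** Appendix G defines progression as a rise of at least 20% over the smallest sum and at least 5 mm. At Day 46 the only earlier sum on the protocol schedule is baseline, so the rise needed is max(5, 0.2 × S), where S is the baseline sum. Partial response needs a fall of 0.3 × S. The values of S are assumptions.

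| Sum S (mm) | Rise for PD (mm) | Rise in biopsied lesion if it is the only target | Rise in biopsied lesion if it is half of S | Fall for PR (mm) |
|---|---|---|---|---|
| 20 | 5 | 25% | 50% | 6 |
| 25 | 5 | 20% | 40% | 7.5 |
| 50 | 10 | 20% | 40% | 15 |
| 100 | 20 | 20% | 40% | 30 |

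For a fall to reach PR, the biopsied lesion must shrink by 30% if it is the only target, or by 60% if it is half of the sum.

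**Step 5: which endpoints move.**
- PFS (exploratory): a false progression at Day 46 is an event with no confirming scan.
- ORR (secondary): a patient moved from stable disease to progression was a non-responder before and remains one. ORR changes only if a false progression comes before a true response that is then not counted, or if lasting scarring gives a 30% fall that is still present at the confirming scan.
- Primary CD8 endpoint and OS: neither uses the target sum.

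**The case against.** The causal premise is not in the documents. Nothing there says that coring changes a lesion's longest diameter, by how much, or for how long, and the scan comes at least 15 days after the last biopsy. The change needed grows with the sum, so a patient with bulky disease is hardly exposed. This stands, and it limits the point to an inexpensive precaution.

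A reader might infer that a 5 mm haematoma in one patient would shift the response rate by 1/15 = 6.7 percentage points. The documents do not support that. Stable disease and progression both count as non-response, and Appendix G lists an unconfirmed response as stable disease. Section 16.1 and Appendix G disagree on the minimum confirmation interval (4 weeks against 6) and should be reconciled, but both ask for confirmation.

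Size is also not the only selection criterion. Appendix G mentions suitability for accurate repeated measurement, which gives a careful reader some room to prefer an unsampled lesion. It does not mention biopsy and does not require that choice.

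A reader might take the radiotherapy clause in Section 10.3 to make the silence on biopsy a contradiction. It does not: radiotherapy is an anti-tumour treatment and needle sampling is not. The clause shows only that the plan saw a need to protect target lesions from one local intervention.

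Finally, PFS is exploratory and is described by Kaplan-Meier in a single arm without a formal comparison, so one wrong event date has limited consequence. That also stands.

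**Conclusion.** The gap is real and small. The plan allows a lesion sampled at least ten times to be a target lesion, and requires this in patients with one or two measurable liver lesions. At least the second sampling always falls between the baseline and Day 46 scans.

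The main exposure is a false, unconfirmed progression in exploratory PFS. It matters mostly when the biopsied lesion is the only target or dominates a small sum: 5 mm is enough for a sum of 20 to 25 mm, against 10 mm for 50 mm and 20 mm for 100 mm. These figures rest on assumed lesion sizes. The frequency of a procedural change that large is unknown from the documents and, in my judgement, probably low.

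ORR is exposed only by the two narrow routes in Step 5. The primary endpoint, its sample size and OS are untouched. This is an improvement worth making because it costs little, not a flaw that threatens the trial's conclusions.

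**What to change.** Amend Appendix G for patients still to be enrolled:

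- Where another measurable lesion exists, the research-biopsy lesion is not chosen as a target. It is followed as non-target, and its diameter is still recorded at each assessment but left out of the sum.
- Adjust the sentence that takes in all measurable lesions, which would otherwise contradict this rule. Widen the non-target definition as well: it now covers only small or non-measurable lesions and says that non-target lesions are not measured. Keeping the diameter preserves the link between the CD8 change and the size change in the same lesion.
- Where the biopsied lesion is the only measurable one, and for patients already enrolled, flag it. Report ORR and PFS a second time with that lesion removed from the sum, or without the patient if it is the only target. For enrolled patients this requires that the sampled lesion can be identified from the records.

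Separately, reconcile the second biopsy day in Sections 9.2 and 10.4.

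The cost is a few sentences, fewer target lesions in some patients and one small sensitivity analysis. No visit, sample or primary analysis changes. The rule does not remove every trace of the problem: a scar in a non-target lesion could still prevent a complete response, and non-target progression rests on the treating physician's opinion. Appendix G does at least ask for that progression to be confirmed later.

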Appendix H

Celecoxib Patient Diary

Protocol # _____
Drug Name: Celecoxib
Treatment Week: _____

Patient Name: _____
Med. Record #: _____

Study Medication Calendar

You are participating in a study that requires Celecoxib 200 mg to be given twice daily, approximately 12 hours apart for three consecutive days. This dose will be given three days a week for three consecutive weeks. Your morning dose of Celecoxib will be given to you along with your pre-medications while you are in clinic. Please complete this calendar to document your evening doses of Celecoxib. Your nurse will let you know what time you receive your morning dose of Celecoxib so you can take your evening dose approximately 12 hours after.

Day			
Dose			
Time			

Please remember to bring this calendar and your pill bottle (including any unused pills) with you to your next study appointment.

Coordinator use only

Date of return: _____

of pills

(dispensed: _____ -- returned: _____) $\times 100 =$ % adherence: _____
_____ # of pills scheduled _____

Patient signature: _____

Date: _____

Investigator signature: _____

Date: _____

Clinical Research Services

PROTOCOL TITLE: Phase 2A Study Evaluating a Chemokine-Modulatory Regimen in Patients with Colorectal Cancer Metastatic to the Liver

Appendix I
Creatinine Clearance Calculation

Cockcroft-Gault Equation*

Men: $\text{CrCl} = [(140 - \text{YR}) \times \text{weight in kg}] / (\text{PCr} \times 72)$

Women: $\text{CrCl} = 0.85 \times [(140 - \text{YR}) \times \text{weight in kg}] / (\text{PCr} \times 72)$

Where:

CrCl is creatine clearance (mL/min)

PCr is plasma creatinine (mg/dL)

YR is age (years)
